1. STUDY SYNOPSIS

Study title	Does early mobilisation after Ankle fracture surgery enhance Recovery ? A pragmatic multi-centre randomised controlled Trial with qualitative component and health economic analysis comparing the use of plaster versus removable support boot (ART).
Short study title:	The Ankle Fracture Recovery Trial (ART)
Study design	This study is designed as a pragmatic multi-centre randomised controlled trial with qualitative component and health economic evaluation comparing plaster cast and support boots as methods of post-operative ankle fracture management.
Study participants	
Inclusion Criteria
 
 • Received surgery for fixation of unstable ankle fracture • Provision of informed consent to participate 
Exclusion criteria
 
 • Under 16 year olds (skeletally immature). • Poor skin condition at operation site. • Serious concomitant disease (e.g. stroke, osteoporosis, arthritis). • Diabetic neuropathy/other sensory neuropathy (lack of sensation). • Non-ambulatory prior to injury. • Active leg ulceration. • Patients who are unable to understand the study information or unable to complete the outcome questionnaires. • Surgeon concerned about quality of fixation/integrity of wound. • Fracture requiring further stabilisation in/around the ankle (e.g. syndesmosis). • Open ankle fracture (bone broken through skin). • Participant is a participant in other concurrent interventional research which may over-burden the participant or confound data collection. • Concomitant injuries which will have a confounding effect on rehabilitation in the opinion of the investigator.
Number of participants	276 patients in total (138 in each treatment group).
Follow-up duration	Patients will be followed up in clinic at 4 weeks post-baseline (6 weeks post-operatively) and via questionnaires), at 5 weeks post-baseline (7 weeks post-operatively) and 10 weeks post-baseline (12 weeks post-operatively). Qualitative telephone interviews with up to 20 participants will take place after the 10-week follow up.

Planned study period	48 months (37 month recruitment period)
Study aim	To evaluate the relative effectiveness and cost-effectiveness of two methods of post-operative ankle fracture management (plaster versus removable support boot allowing range of movement) and to provide evidence-based recommendations for best care in clinical practice.
Study objectives	
 1. To determine whether there is a difference in ankle function between the two types of treatment. 2. To determine whether there is a difference in quality of life between the two treatments. 3. To estimate which is the cost-effective treatment option to inform decision-making. 4. To explore patient experiences and the psychological and social impact of their treatment.
Outcome measure data	
Primary outcome: The primary outcome measure for this study is the Olerud and Molander ankle score at five weeks after randomisation.
 
Secondary outcomes:
 
 • Ankle functional data (range of movement, weight-bearing) • Standardised measure of general quality of life (EQ-5D-5L) • Healing status • Complications • Return to Usual Activities 
Other data collected;
 
 • Baseline characteristics • Healthcare resource use • Adverse events • Mobilisation and adherence to exercise
Qualitative component	
Telephone interviews conducted at around the 10 week follow up time point with up to 20 participants to address:
 
 • Experiences of each type of treatment (plaster/boot). • Lifestyle implications – individual (e.g. washing), family, social, psychological, work, financial, residential, diet, transport (e.g. driving), leisure activities, and independence. • Expectations, mind-set, confidence, including the perceived views of carers where appropriate.
Interventions	
Patients will be allocated in a 1:1 ratio with both groups weight-bearing as tolerated:
 
 1. Plaster below knee i.e. immobilised for four weeks. 2. Removable support boot with range of movement for four weeks.

2. ABBREVIATIONS

AE	Adverse Events
BUCRU	Bournemouth University Clinical Research Unit
CI	Chief Investigator
CEAC	Cost Effectiveness Acceptability Curves
CRF	Case Report Form
DVT	Deep Vein Thrombosis
HE	Health Economist
ICER	Incremental Cost Effectiveness Ratio
ICH GCP	International Conference on Harmonisation, Good Clinical Practice
IEP	Image Exchange Portal
INMB	Incremental Net Monetary Benefit
ISRCTN	International Standard Randomised Clinical Trial Number
NIHR	National Institute for Health Research
OMAS	Olerud and Molander Ankle Score
PenCTU	Peninsula Clinical Trials Unit
PI	Principal Investigator
PSS	Prescribed Specialised Services
QALY	Quality Adjusted Life Years
RCT	Randomised Controlled Trial
REC	Research Ethics Committee
RfPB	Research for Patient Benefit
SAE	Serious Adverse Events
TMG	Trial Management Group
TSC	Trial Steering Committee
WPAI	Work Productivity and Activity Impairment Questionnaire

3. INTRODUCTION

Approximately two million ankle fractures occur annually in the United Kingdom affecting 3.6% of the population, 75% in under 60 year olds¹, of which a high proportion need surgical fixation, with considerable cost to the National Health Service. Indeed, 7.2% of all fractures admitted to Poole Hospital are ankle fractures and 197 underwent surgical fixation in 2011² illustrating the scale of the issue (audit data suggest 104 in Basingstoke in 2012 and 76-80 in six month periods in 2009 and 2010 respectively in Portsmouth). Ankle fractures are a cause of short-term and sometimes long-term disability and pain. These injuries frequently require many weeks off work with subsequent economic consequences³. Six weeks of immobilisation in plaster is frequently advocated for all ankle fractures *not* requiring surgery. It is also recognised practice to immobilise a broken ankle after surgery for comfort, support and to allow the wound to heal. This tends to be with a plaster because it is cheap and readily available in the operating theatre and has been used for decades.

However, there has been no consensus for the management of ankle fractures post-operatively for those ankle fractures that need surgical fixation. Therefore, current treatment is not standardised in many Trusts in the National Health Service. There is evidence to suggest that removing plasters and wearing removable boots that allow early weight-bearing and range of movement of the ankle, maximises rehabilitation potential.

A number of studies have investigated the benefits of early weight-bearing and mobilisation following ankle fracture fixation. Early return to function should be the principal goal following surgical management³. Traditionally, patients have been managed in a plaster cast and have been strictly non-weight-bearing (hopping on their unaffected leg).

However, immobilisation can result in reduced range of movement and muscle deterioration⁴⁻⁶. Early mobilisation of ankles following open reduction and surgical internal fixation provides short-term benefits in improved range of movement, reduced swelling, pain, an earlier return to work, improved patient satisfaction, and better ankle function⁷.

At Poole Hospital, fitting patients with a plaster following open reduction and surgical internal fixation costs approximately £20.84 for materials plus plaster technician labour costs for 10-15 minutes per case. Although there are a range of boots available on the market at varying prices, those used are chosen for their quality and value for money – for example, the pneumatic walker boot currently in use at Poole Hospital costs £52.39 and we expect it may be equally labour intensive (information provided by plaster technicians).

However, the boot may be more comfortable as it can be removed at night and for washing, and ultimately improves patient satisfaction⁸. Despite boots having fewer limitations than plaster, they can still be considered cumbersome and disposal of plasters and boots both have environmental impact.

Furthermore, some studies report conflicting and inconclusive findings with regards to complications. Lehtonen et al⁹ found wound infections in 6.6% of those who mobilised early and a high incidence of deep vein thrombosis. On the other hand, Vioreanu et al⁶ found patients who exercised once primary wound healing had taken place had fewer wound infections and the immobilised group had problems with deep vein thrombosis. Farsetti et al¹⁰ compared two case series of 22 patients and found no correlation between wound complications and continuous passive movement applied for the first three weeks post-operatively.

Although there are two current trials underway, one in London¹¹, the other in Toronto¹², the London study is a smaller study (n=76) and does not encourage active movement through range of movement exercises whilst the Toronto study is unrealistic not allowing weight-bearing in plaster. The most recent systematic review by Thomas et al³ (p 674) and a Cochrane report by Lin et al¹³ (p 431), both recommend the need for more research with well-designed and conducted trials with adequate numbers and reporting. There is limited evidence supporting the use of a removable type of immobilisation and active range of movement and no previous studies, to the research team's knowledge, have investigated the socio-economic factors and psychological impact which may be related to return to function, independence, and work.

This research is needed now to ensure that the post-operative management of patients who have sustained an ankle fracture is consistent with best practice and considerate of patient experience. The research is particularly timely in this economic climate to allow patients to optimise their rehabilitation potential and return to full function and normal employment as soon as possible. There is currently no definitive study advising on the optimal treatment and rehabilitation of ankle fractures following surgery. This randomised study aims to objectively provide an answer. In particular, the study will provide guidance on which form of post-surgical treatment is more reliably able to restore an individual's independence, function, and mobility after ankle fracture surgery; as well as the probability of being a cost-effective treatment option for the NHS. It will also investigate whether the treatment regime influences a patient's return to work as well as exploring the wider socio-economic implications of the two treatments.

As part of patient and public involvement for the design of this study, twelve telephone consultations were conducted with service users who had received treatment for ankle fractures. One of the most important issues to patients suffering from ankle fractures was the lack of hygiene when immobilised in a plaster. The advantage provided by a removable boot in terms of being able to visualise and mobilise tissues and joints has been alluded to in several studies.

If there is a clear advantage of one treatment over another in terms of outcomes and costs, then treatment can be standardised with recommendations being made for local and national policy guidelines. This will directly benefit patients, employers, healthcare providers and the wider economy.

4. AIMS AND OBJECTIVES

4.1. Aim

To evaluate the relative effectiveness and cost-effectiveness of two methods of post-operative ankle fracture management (plaster versus removable support boot with range of movement) and to provide evidence-based recommendations for best care in clinical practice.

4.2. Objectives

4.2.1. Primary objective

- To determine whether there is a difference in function between the two types of treatment.

4.2.2. Secondary objectives

[figure not shown]
- To determine whether there is a difference in quality of life between the two treatments.
- To determine whether there is a difference in healing, complications and adverse events between the two treatments.
- To determine whether there is a difference between return to work, driving and usual activities between the two treatments
- To determine which is the most cost-effective treatment option if provided in the NHS.
- To explore patient experiences and the psychological and social impact of their treatment.

5. STUDY DESIGN

5.1. Study design overview

This study is designed as a pragmatic multi-centre randomised controlled trial with qualitative component and health economic evaluation comparing plaster cast and removable support boots as methods of post-operative ankle fracture management.

Figure 1 Study design flowchart
 Illustrating flow of patients through the trial and the time points for data collection.

¹ Patients not requiring surgery, or who are ineligible or unwilling to participate in the trial will be excluded from the trial and managed as per usual care.

5.2. Design and bias considerations

The nature of the two interventions clearly makes it impossible to blind the patient or treating clinicians. Moreover the appearance of the leg at the follow-up appointments will make the allocation evident, so that those involved in outcome assessment also cannot be blinded. However, the trial statistician and data analysts will remain blinded to group allocation until the analyses are completed. Furthermore, the radiographic evaluations of healing status performed by the Chief Investigator at the end of the study (see section 9.8 Radiographic Evaluation) will be performed in a blinded manner.

5.3. Duration of patient participation

The expected duration of patient participation is approximately 10 weeks starting from randomisation and collection of baseline measures at the first clinic visit. Up to twenty participants will be selected for qualitative interviews soon after the 10-week time point. End of patient participation will be defined as the completion of data collection for the last patient followed-up in the study.

6. SETTING

The study will be conducted at three investigator sites initially; Poole Hospital NHS Foundation Trust, Basingstoke and North Hampshire NHS Foundation Trust and Queen Alexandra Hospital, Portsmouth Hospitals NHS Trust. Other sites may be invited to participate in the event that recruitment rate is lower than anticipated, subject to REC and NHS approvals. Conduct of the trial at each site will be led by a local Principal Investigator with support from research personnel trained in good clinical practice. Support will also be required from a physiotherapist(s) to perform protocol-specific clinical assessments, for which training will be provided.

7. OUTCOME MEASURES

This section is intended to list, describe and justify choice of outcomes rather than to describe how the data are collected for research purposes. Data collection is addressed in Section 9.

7.1. Primary Outcome measure

The primary outcome measure for this study is the Olerud and Molander¹⁴ ankle symptom scale at five weeks after randomisation. The five week post-baseline data collection period is the critical period, as this is when it is anticipated that the group who had boots will have a greater level of function^{3,6}. Most patients in both groups will no longer be using their allocated treatment and will have had at least 3 days without a plaster cast or boot to enable functional recovery of the ankle to be assessed. The study will also compare the ten week Olerud and Molander¹⁴ ankle score to check whether any differences between groups still remain, and to see whether the ten week measures have returned to their (estimated) pre-injury values.

7.2. Secondary outcome measures

7.2.1. Functional data

Functional data including range of movement (dorsiflexion, plantarflexion, inversion, eversion (degree angles)), circumferential swelling and weight-bearing status at four weeks post baseline. Range of motion will be assessed using a goniometer. Weight-bearing will be classified as touch weight-bearing, partial weight-bearing or full weight-bearing. Circumferential swelling of the injured ankle will be measured using a tape measure. Circumference of the non-injured ankle will be measured in the same way and used as a comparison. Range of movement assessments and circumferential measurements must be conducted by a physiotherapist trained in the requirements of the study protocol and recorded in the patient's medical record.

7.2.2. Healing status

Healing status will be determined by the Chief Investigator's blinded review of pre-operative, intra-operative and post-operative X-ray films at the end of the study (see section 9.7 Radiographic Evaluation). The review will evaluate integrity of the surgical metal work (displaced / undisplaced) and whether or not there is evidence of fracture healing at the 4 week time point.

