9.3.7. End of baseline visit procedures

The research team will ensure the following before the patient leaves the hospital:

- The baseline questionnaires are as complete as possible. If data are missing, any missed questions will be highlighted to the patient.
- The patient has the correct advice leaflet (according to their treatment allocation) and the Patient Diary.
- The patient is aware of when their next appointment is scheduled.

A member of the research team will subsequently ensure that:

- The patient's participation in the trial is appropriately recorded in the hospital records and that hospital notes are labelled / annotated in accordance with local practice.
- The CRF with data collected on delivery of treatment is completed.
- The approved GP letter is sent to the patient's General Practice.

The original completed questionnaires and CRF pages will be sent to PenCTU using FREEPOST envelopes – copies of these should be retained at the local site.

9.4. 4-week follow-up visit (6 weeks post-surgery)

Participants in both treatment groups will attend a routine six-week post-operative appointment. Participants will have their plaster or support boot removed (unless otherwise indicated), routine clinical assessments and x-rays will be performed to guide the participant's subsequent management. 4-week follow up data will be collected at this visit.

9.4.1. 4-week follow-up questionnaire completion

The participant will be provided with a questionnaire to be completed during the visit. The 4-week questionnaire booklet will comprise:

- EQ-5D-5L (see section 7.2)
- Resource use questionnaire (see section 7.4)

Participants will be encouraged to use their Patient Diary to facilitate answering questions as appropriate.

9.4.2. 4-week follow-up CRF completion

Following removal of the plaster or support boot, the patient will receive routine clinical assessment and a member of the research team will transcribe the following information from the patient's hospital records into the trial case report form (CRF):

- Range of ankle movement (see section 7.2)*
- Weight-bearing status (see section 7.2)
- Circumferential swelling (see section 7.2)*
- Complications and associated antibiotic usage (see section 7.2)
- Time required to remove boot/ or plaster and re-fit if necessary (see section 7.4)
- Mobilisation and adherence to exercise (see section 7.7)

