9.8. Radiographic Evaluation

Pre-operative, intra-operative and post-operative X-rays will be taken for each participant as per routine care. In some cases, particularly where recovery is complicated, further X-rays within the 12-week trial period may also be taken. At the end of the study, pre-, intra- and post-operative X-rays, plus any further X-rays taken within the trial period will be reviewed by the CI in a blinded fashion on a participant-by-participant basis. For each participant, the CI will record the following on a bespoke data collection form:

- Fracture classification (Weber A, B or C)
- Fracture pattern (medial malleolar fracture or deltoid ligament injury)
- Integrity of surgical metalwork (displaced or undisplaced)
- Evidence of post-operative fracture healing (yes/no)

The data collection forms will be returned to the CTU for entry into the trial database. Research teams at local sites will liaise with their X-ray departments to arrange anonymisation and transfer of images. Instructions of procedures by which X-rays are collected, labelled, stored and sent are detailed in a separate work instruction.

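### Fracture healing is defined at 4 weeks in section 7.2.2, but section 9.8 takes one undated reading from all films up to 12 weeks, so patients with extra films can be judged later than the rest

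*Protocol*

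**What the plan says.** **Outcome definition (section 7.2.2).** Healing status comes from the Chief Investigator's "blinded review of pre-operative, intra-operative and post-operative X-ray films at the end of the study". The reader assesses metalwork ("The review will evaluate integrity of the surgical metal work (displaced / undisplaced") and, in the same sentence, "whether or not there is evidence of fracture healing at the 4 week time point".

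**Reading procedure (section 9.8).** The set of films is wider: "In some cases, particularly where recovery is complicated, further X-rays within the 12-week trial period may also be taken". The review covers the pre-, intra- and post-operative films "plus any further X-rays taken within the trial period will be reviewed by the CI in a blinded fashion". Among the items on the form are "Integrity of surgical metalwork (displaced or undisplaced" and "Evidence of post-operative fracture healing (yes/no". Neither item carries a time point, and nothing says which film decides when there are several.

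**Schedule (Table 1).** Healing status appears only in the End of Study column, with a footnote pointing to the blinded review.

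**Analysis (section 12.2.3).** Both items are categorical outcomes for logistic regression adjusted for site, age and fracture complexity. No time point is given.

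**Availability of a 4-week film (section 9.4).** At the 4-week visit, for both groups: "Participants will have their plaster or support boot removed (unless otherwise indicated), routine clinical assessments and x-rays will be performed".

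**The concern.** The definition fixes one time for everyone. The procedure lets the evidence vary with the patient's course: an uncomplicated patient is read on films up to the 4-week visit, while a patient with a complicated recovery may also be read on films taken up to 12 weeks after surgery. Having later films is a consequence of what happens after randomisation, and the treatment may influence it. Section 10.3 itself expects the problems to differ somewhat between plaster and boot.

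Two distortions are then possible. A fracture not yet healed at 4 weeks but healed on a later film could be recorded as healed, which would mask slow healing in the arm with more complicated recoveries. Late displacement of metalwork could be seen on film only in patients who were re-imaged. If one arm is re-imaged more often, either effect can appear as a treatment difference.

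The between-group comparison of healing is a stated secondary objective (section 4.2.2). It also rests on the only outcome assessment described as blinded (section 5.2). The problem arises when the data are recorded: if the form holds one undated answer, no later analysis plan can recover the 4-week status from it.

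**Working it through.** The protocol gives no figure for this outcome, so there is nothing to reproduce. Its one power calculation (204 with complete data, section 12.1) concerns the ankle score and has no bearing here. The check is a comparison of text, followed by timing and an illustration of size.

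**1. The sections side by side**

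| Place | Films | Time point for healing | Time point for metalwork |
|---|---|---|---|
| 7.2.2 | pre-, intra-, post-operative | 4 weeks | unclear: same sentence, but the time phrase follows healing |
| 9.8 | the same, plus any further films in the trial period | none | none |
| Table 1 | X-rays reviewed at end of study | none | none |
| 12.2.3 | not stated | none | none |

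Read alone, the term post-operative in 7.2.2 could stretch to any film after surgery. Section 9.8 lists further films separately from post-operative ones, so the wider reading is available in the procedure and is not excluded anywhere.

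**2. Timing** (synopsis and Table 1)

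- Week 4 after baseline is week 2 + 4 = 6 after surgery.
- The trial period ends at week 2 + 10 = 12 after surgery.
- Largest gap between the defined time point and a later film: 12 − 6 = 6 weeks.
- Counted from randomisation, observation runs to 4 weeks for most patients and up to 10 weeks for re-imaged ones: 10 / 4 = 2.5 times as long.

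**3. Possible size (assumed inputs)**

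Let p be the share of an arm with later films. Let g be the rise in the chance of being recorded as healed (or displaced) if the later film decides, among those patients.

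- Shift in that arm's proportion = p × g.
- Between-arm bias = p₁g₁ − p₂g₂.

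The protocol gives neither p nor g. Over an assumed range:

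- Low end: 0.02 × 0.20 = 0.4 percentage points.
- High end: 0.20 × 0.60 = 12 percentage points.

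Between arms:

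- Displacement, p of 20% against 10%, g = 0.10 in both: 2% − 1% = 1 point. That is 0.01 × 102 = 1.0 to 0.01 × 138 = 1.4 patients, using the per-group figures for complete data (section 12.1) and for recruitment (synopsis).
- Healing, p of 20% against 10%, g = 0.40 in both: 8% − 4% = 4 points.
- Equal p and equal g in both arms: 0 points.

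**The case against.** The best defence is that the sections can be read together. Section 7 says it describes outcomes and leaves data collection to section 9. On that reading, 7.2.2 sets the time point and 9.8 only lists the films to hand and the items on the form. The form and the analysis plan, neither of which is shown, may fix the rest. Section 9.6.2 expects only a small proportion of patients to need further evaluation at 12 weeks after surgery, and failure of fixation is collected separately as a complication (section 7.2.4).

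Much of this stands, and it rules out three stronger readings that a reader might infer.

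- **That a patient unhealed at 4 weeks but healed later will be scored as healed.** Section 9.8 does not say that the latest film decides, and a further film could even predate week 4. The text supports only that such a patient can be judged later.
- **That metalwork status is also clearly fixed at 4 weeks.** The time phrase in 7.2.2 attaches most directly to healing. For metalwork the fault is an unstated time point, not a clear contradiction.
- **That blinding fails because a retained cast or boot shows on the film.** The protocol does not say that films are taken through a device. It also does not say that a device kept after week 4 matches the allocation, and knowing that recovery was complicated does not reveal the arm. At most, a device may be visible on some films.

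What the defence does not remove is that the reading procedure admits later films, asks for a single answer and gives no rule for choosing between films. The separate work instruction mentioned in 9.8 covers collecting, labelling, storing and sending films, not reading them.

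**Conclusion.** The inconsistency is real. Healing is tied to 4 weeks in its definition and to no time at all in the procedure, the schedule and the analysis text. The procedure also brings in films that exist selectively in complicated recoveries. Outcome ascertainment can therefore depend on the patient's course.

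The size is unknown. The illustrated shifts rest on assumed re-imaging and reading rates and on the assumption that the later film decides. Bias arises only if the frequency or the content of later films differs by arm. The primary outcome and the sample size are not touched. The point should be settled before any film is read, because it concerns what is recorded and cannot be repaired afterwards from one undated answer.

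**What to change.** Reconcile section 9.8, Table 1 and section 12.2.3 with section 7.2.2:

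- Score healing from the routine 4-week film, with earlier films for reference, before any later film is viewed.
- State the same time point explicitly for metalwork integrity in 7.2.2 and 9.8.
- Record findings on later films in separate fields with the film date, and report them descriptively.
- Name the 4-week time point in Table 1 and in the analysis text.
- Correct the cross-references in 7.2.2 and 7.3.2, which cite section 9.7; Radiographic Evaluation is section 9.8.
- Optionally, note on the form whether a cast or boot is visible.

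The cost is small: a few fields and a reading order on a form that is already bespoke, with the same reader and the same films, since both groups have X-rays at the 4-week visit. The downside is that late displacement leaves the main radiographic outcome. It is still captured in the dated later-film fields and, up to 12 weeks after surgery, as the complication failure of fixation.
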